Direct Contact: Neurologists may discuss the study with their patient/prospective subject (in person/via telemedicine or by telephone) and provide the study physicians contact information, to interested individuals. They may also obtain the patient's permission to be contacted by study staff. Any contact between study staff will take place with NYU HIPAA compliant email or telephone. Screening procedures have been identified earlier in the protocol.

Physicians will not be contacted if their patients choose to participate because a) they will all have been informed about the study before the study begins and b)it is a minimal risk study which should not interfere with the treatment plan.

Indirect Contact: Through the Epic research team, we will generate a list of people who were seen with headache or migraine in the past 6 months in the practices named above (Neurology, Primary Care and Urgent care) who are between ages 18-80 and who have not opted out of being conducted for research at NYU.18–80 years; Study team members will then pre-screen those to determine whether they might meet migraine criteria based on the International Classification of Headache Disorders (ICHD) criteria; Migraine Disability Assessment (MIDAS) score >5. 4+ headache days a month In addition, the following PHI will also be captured in the EPIC data pull: subject name, date of birth, MRN, telephone number, email address, medical records such as admission/discharge dates.

The following team members will have access to the EPIC search results: Principal investigator, biostatistician, research volunteers, research coordinators, and data analysts. The study team will search EPIC daily over the course of the study (12 months). As discussed above, the research team (pain and volunteers) will undergo rigorous training in study procedures.

For focus group: study team members will use the focus group recruitment announcement email or telephone script to find out if enrolled subjects would be willing to participate in a focus group on what they thought of the study.

As stated above, once contact is made, approved recruitment language will be used to communicate the reason they are being contacted and subjects will be asked if they are interested in participating in this specific study via telephone or email. Should the potential subjects agree, the study team will provide the subjects with information regarding the next steps for participation. Any contact between study staff and potential participants will take place with NYU HIPAA compliant email, [contact] or through REDCap. Any recruitment information sent by email will utilize Send Safe email.

If a subject requests information regarding opting out of further recruitment for all research, subjects will be directed to contact study coordinator or have subjects contact [contact] or [name].

Initial Screening Questions for Chronic Post-traumatic headache:

When did you have your injury that led to concussion symptoms? Did you develop headaches

afterwards from the injury? If so, when did you first develop the headaches? (Eligible would be 3-12 months post initial injury)

On a scale of 0-10, what is your average headache intensity? Maximum headache intensity?

Do you own a smartphone? Yes/no

Would you be interested in doing daily exercises to treat your headaches? Yes/no

If they meet criteria, when they come for the NYU Concussion Center appointment, they will be scheduled for a session with the RA to discuss the study, obtain informed consent in interested subjects, complete the REDCap survey, and download the app.

ProcessofConsent

Research volunteers or physicians who are study members will obtain consent. As indicated above, research volunteers will be trained during an intense one week training on study procedures including an emphasis on how to consent the participants. This is a no risk/very low risk study unlike other interventional studies. Thus, it is appropriate for trained research volunteers to consent these participants just as they would be able to do so for survey type studies. They will be carefully observed during the initial consent process to ensure that they

are doing it correctly. They will explain the rationale for the study (see above) and review the form with potential subjects. We will file an IRB addendum later on to add them to the protocol.

For focus group: subjects will sign an informed consent form in-person at the focus group meeting.

SubjectCapacity

Only subjects with capacity will be asked to participate in the study.

Subject/RepresentativeComprehension

Subjects will be asked to explain that they understand that they may or may not be offered this additional intervention and that the determination of whether they are offered it is random.

Subjects will be asked to explain that they understand that they will be asked to do a daily relaxation exercise and that they will be asked to record their headache characteristics, mood, anxiety and stress levels on the smartphone app as well as the number of hours that they slept/sleep quality.

DebriefingProcedures

N/A

Data Safety Monitoring Plan

The PI will be responsible for data safety monitoring. This is a minimal risk device. Minimal to no risk is expected for participants in the study. Only the PI, RVs and any future co-investigators will have access to the data. Co-ls would be added to the IRB at a later date. No personal/identifying information will be kept on an insecure site. No personal or identifiable information will be stored within the app. The PHI will be stored in REDCap. We will report all unanticipated events within a 24- to 48-hour time window or as soon as possible. There are no predetermined criteria for action.

ConsentForms

A consent form for each subject will be obtained. Please see attached.

Documentation of Consent

The documentation will be kept in a locked storage unit in [name] office on the 14th floor of the Department of Neurology, [name].

PaymentforParticipation

There is payment for participation for all subjects. They will receive \$25 for the initial survey and then \$1/day for up to 60 days (the initial 60 day period) for data entered. If they complete 80% or more of the initial 60 day period, then the daily amount paid will be doubled. In addition, they will receive \$15 for the one month and two month followup email or call and \$25 for the 3 month and 6 month followup email or phone assessments. The maximum amount they can be paid is \$225. The subject reimbursement amount is commensurate with other headache related smartphone application studies throughout the country.

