Aim 1: Conduct a feasibility and acceptability study of the RELAX approach in migraine and post-traumatic headache (PTH) patients who visit the NYU Department of Neurology General Practice and/or subspecialty groups or the NYU Concussion Center. We will recruit and randomize subjects (N=400) in the FGP Neurology Group including the MS Center and Headache Center and the NYU Concussion Center to receive the RELAX intervention or monitored usual care (MUC). Both groups will be asked to complete daily diaries, and data will also be collected on measures of recruitment, retention, adherence, and satisfaction with the PMR, the clinically important endpoint. With the PMR, we hypothesize that at least 70% of participants will be adherers (e.g., use RELAXaHEAD at least 4 days/week for 12 weeks). We will assess if the daily diary is acceptable by examining whether there is differential attrition with daily diary completion. We hypothesize no difference between the two groups for acceptability of the diary. We will define acceptability as an average score of ≥4 (0-5 Likert scale) on the 9-item acceptability questionnaire. The outcomes for Aim 1 are the feasibility/acceptability outcomes; number of days of diary entered, number of days of pmr, time spent/day on pmr (Please refer to Table 2)

Aim 2: Conduct within group analyses of the RELAX approach vs MUC.

In the migraine patient population, the primary outcome will be migraine quality of life and migraine disability measured by Migraine Quality of Life (MSQ) and the MIDAS. In the migraine-MS population, a primary outcome will also be MS pain related disability as measured by the MOS Pain Effects Scale (PES). ¹⁵ Secondary outcomes include headache frequency and intensity, stress levels, sleep and psychiatric screens (NIH PROMIS depression and anxiety screens). We hypothesize that at 3 months compared with baseline there will be trends in the RELAX arm towards decreased disability (as measured by the Migraine Disability Assessment Scale (MIDAS)) and improvements in MS pain related quality of life in the MS-migraine patient population.

In the PTH patient population, we will examine the secondary outcomes noted above.

Background

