Neurology Urgent Care Practice: At this time, there is no epic code listed as part of the Neurology Urgent Care visits so an epic report cannot be generated as in the cases above. However, the Neurology FGP maintains a list of the patients seen through the Neurology Urgent Care Practice. On a weekly basis, this list will be sent by a FGP administrator to the epic research team and the patients will be screened based on the study eligibility as described in the irb (diagnosis of "headache" and age 18-80). If these patients meet study eligibility and have not opted out of being contacted for research purposes, then they will be forwarded to [name] research team. The Epic data lists will be generated weekly and potential subjects will be screened and contacted on a near daily basis. A record will be made in RedCap, a HIPAA compliant database, using de-identified info for all those who screen in and those who screen out. For those who screen in and decide to enroll in the study, an identified record will be created in RedCap.

We had recruited participants who had called the NYU Concussion Center. However, recruitment for this arm of the study is closed at this time. We had also recruited patients with Multiple Sclerosis and headache and recruitment has closed at this time.

Screening will be done by IRB approved members of the study team. This includes both paid staff and NYU nontraditional volunteers.

The NYU Headache Research Program has been recognized for its solid training of pre-health students in research methods. In fact, it received the first ever City College of New York S Jay Levy Fellowship for Future Leaders Distinguished Internship Site Host Award (2017-2018).

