The total N will be 490. We had an initial approval for N=402. Going forward, we are hoping to recruit an additional 90 subjects from the FGP Urgent Care Center and from the Neurology Urgent Care Center.

The initial stats were calculated as follows:

Sample size: Phase 1: 432 subjects, Phase 2: 90 subjects

Phase 1: The NCCIH uses the Kramer reference for power calculation. As indicated by Kraemer and colleagues, our pilot sample size (402) is based on the pragmatics of recruitment and the requisites for examining feasibility. We anticipate an adherence rate of at least 70%. If the adherence rate is below 50%, we will consider the approach in need of further refinement. Thirty patients per arm will allow estimation of an exact 95% confidence interval whose lower bound exceeds 50%. Therefore, insufficient adherence would be ruled out, assuming the true adherence rate is 70% or greater. This approach obviates the need to handle missing data, because subjects who drop out will be assumed non-compliant.

Thus, we plan to try to enroll migraine patients from the general neurology group, the NYU Headache specialists within the main academic center ([name]/ACC), the NYU Headache Center in the Men's Health Center and from [name] office. We would also like to recruit at MS Society events and other neurology events.

Research assistants will evaluate which patients are eligible to participate based on the inclusion and exclusion criteria stated below.

Phase 2: We arrived at the 90 urgent care subjects based on our initial power analysis and then the NIH's request in the Just in Time to increase the N up to 85.

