Box 1: Inclusion Criteria: Age 18-80 years (age 18-65 in urgent care); Meets migraine criteria based on the International Classification of Headache Disorders (ICHD) criteria; Migraine Disability Assessment (MIDAS) score >5.4+ headache days a month.OR Meets Chronic PTH criteria based on International Classification of Headache Disorders (ICHD) criteria, is 3-12 months post-injury, and there are 4+ headache days a month. Scoring > or = 15 on the ISI. Exclusion Criteria: Patients who have had Cognitive Behavioral Therapy, Biofeedback, or other Relaxation Therapy in the past year; Cognitive deficit or other physical problem with the potential to interfere with behavioral therapy; Alcohol or other substance abuse as determined by self-report or prior documentation in the medical record: Opioid or barbiturate use 10+ days a month; Unable or unwilling to follow a treatment program that relies on written and audio file materials; Not

having a smartphone.

Meets Insomnia criteria based on the Insomnia Severity Index (score > or = 15)

Exclusion Criteria [Box1]

Patients who have had Cognitive Behavioral Therapy,

Biofeedback or other Relaxation Therapy in the past year; Cognitive deficit or other physical problem with the potential to interfere with behavioral therapy; Alcohol or other substance abuse as determined by self-report or prior documentation in the medical record; Opioid or barbiturate use 10+ days a month; Unable or unwilling to follow a treatment program that relies on written and audio recorded materials; Not having a smartphone

VulnerableSubjects

N/A

Methods & Procedures

[Please note that Phase 1 is now complete-we are now in Phase 2 of the study]

For phase 1 of the study, a single arm study was done to assess the feasibility and acceptability of the recruitment process and the app. The duration of this Phase was 6 months. The subjects were asked to use the application for at least 3 months. Compliance was checked during this time and compliance calls were done to remind the subject to use the application. In the latter 3 months we studied if the subjects continued to use the application on their own.

July 2020: We are reopening the Phase 1 single arm study to assess the feasibility of virtual subject enrollment prior to expansion to a larger study. Phase 1 will be conducted as above with a N=30 subjects. The steps will

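### Aim 1 promises 400 randomised subjects, but the only phase documented as a two-arm RCT has 90, and no randomised number is given for MS-migraine or PTH

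*Combined protocol and SAP*

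**What the plan says.** **Purpose of the Study, Aim 1.** "We will recruit and randomize subjects (N=400) in the FGP Neurology Group including the MS Center and Headache Center"; the sentence goes on to the Concussion Center and names RELAX and MUC as the two groups. The Aim carries an explicit between-arm hypothesis: "We hypothesize no difference between the two groups for acceptability of the diary".

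**Purpose of the Study, Aim 2.** The heading is "Conduct within group analyses of the RELAX approach vs MUC". The hypothesis is that "at 3 months compared with baseline there will be trends in the RELAX arm towards decreased disability", with improvement in MS pain-related quality of life in the same sentence. On PES: "In the migraine-MS population, a primary outcome will also be MS pain related disability as measured by the MOS Pain Effects Scale (PES". Table 2 also lists PES under the Aim 2 primary outcome. PTH patients are to be examined on the secondary outcomes.

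**Study Design, recruitment.** Concussion Center recruitment is closed. For MS: "We had also recruited patients with Multiple Sclerosis and headache and recruitment has closed at this time".

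**Study Design, sample size.** The total is 490, the initial approval was 402, and the phases are given as 432 (Phase 1) and 90 (Phase 2). On the 90: "we are hoping to recruit an additional 90 subjects from the FGP Urgent Care Center and from the Neurology Urgent Care Center". The Phase 1 justification refers to 30 patients in each arm.

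**Methods & Procedures.** "For phase 1 of the study, a single arm study was done to assess the feasibility and acceptability". Phase 1 is declared complete, then reopened in July 2020, again single-arm, with 30 subjects. Phase 2 is the two-arm RCT. Its procedures also name primary care and the neurology divisions as sources of patients.

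**The concern.** The Aims tell the reader that about 400 patients across several clinics were randomised. The phase descriptions place a cohort of about that size in a study without a control group and leave 90 subjects in the randomised phase. These statements cannot all be right.

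Two things are at stake. The first is the precision of any RELAX-versus-MUC result, which depends on which number is true. The second is the status of the subgroup objectives. PES is a primary outcome for a population whose recruitment has closed and for which no randomised number appears, and PTH outcomes are promised on the same footing.

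No section confines RELAX-versus-MUC comparisons to subjects randomised together. Without that restriction and a corrected N, change from baseline in single-arm users could be read as a trial comparison. The phases also differ in instructed app use: at least 3 months in Phase 1 against an initial 60 days in Phase 2.

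**Working it through.** **1. The plan's own power figure (Study Design, sample size).** Inputs: difference 5.75 in MIDAS change, SD 7, two-sided 0.05, 30 per group with 25% dropout.
- Evaluable per group: 30 × 0.75 = 22.5, taken as 23.
- Normal approximation: power = Φ(5.75 / (7 × √(2/23)) − 1.96) = Φ(2.786 − 1.96) = 79.6%.
- Exact t calculation: 77.8%.

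The stated 80% reproduces to within rounding and method. The fault is in the design text, not in this calculation.

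**2. The subject counts.**
- 402 + 30 = 432. The Phase 1 figure is the initial approval plus the reopened single-arm group.
- 402 + 90 = 492 and 432 + 90 = 522. Neither equals the stated total of 490.
- 400 + 90 = 490. The total is recovered only by adding Aim 1's 400 to the 90, which suggests that the 400 are subjects other than the Phase 2 group.

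**3. Which subjects are documented as randomised.**

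| Group | Stated N | Stated design |
|---|---|---|
| Aim 1 | 400 | randomised, RELAX or MUC |
| Phase 1, including the 2020 reopening | 432 | single-arm in Methods & Procedures; 30 per arm in the sample-size text |
| Phase 2 | 90 | two-arm RCT |
| MS-migraine | none given | not stated; recruitment closed |
| PTH | none given | not stated; Concussion Center closed, but PTH still an inclusion criterion |

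The documented randomised N is 90, which is 90/400 = 22.5% of the Aim 1 figure.

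**4. What the difference does to precision.** Allocation is not stated, so 1:1 is assumed. The sample-size text reports that about half of participants have full follow-through; this is applied equally to both arms. Detectable difference at 80% power = (1.960 + 0.842) × SD × √(2/n), with n evaluable per arm.
- 90 randomised: n = 45 × 0.5 = 22.5. 2.802 × 7 × √(2/22.5) = 5.85; exact t, 5.98.
- 400 randomised: n = 200 × 0.5 = 100. 2.802 × 7 × √(2/100) = 2.77; exact t, 2.79.
- With n = 22.5, power for the plan's 5.75 is 78.7% (normal) or 76.8% (t).

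**5. Sensitivity (exact t).**
- At 25% dropout instead of half: 45 × 0.75 = 33.75, about 34 per arm, gives 4.8; 200 × 0.75 = 150 per arm gives 2.3.
- At SD 5, the low end of the stated range, results scale by 5/7: 5.98 becomes 4.27 and 2.79 becomes 1.99.

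The detectable difference with 90 is about twice that with 400 in each case.

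**The case against.** The strongest reply is that this is a cumulative protocol. The Aims carry over text from the initial approval, and later sections disclose the phases and the closures. The only between-group calculation uses two groups of 30, so nothing in the power argument relied on 400. That is fair, and it limits the harm. But the Aims are current text, and they do not mention urgent care, the stated source of the 90.

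Four stronger readings are tempting, and the documents do not support them.

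- *That MS and PTH patients were never randomised.* The closure text does not say in which phase or design they were enrolled, and the Phase 1 sample-size text speaks of arms. That phrase may be loose, because the adherence interval it justifies needs only one group using PMR, but it cannot be dismissed. PTH remains an inclusion criterion, MS is not an exclusion, and the sample-size section still mentions recruiting at MS Society events.
- *That only urgent-care patients can be in the RCT.* The 90 are attributed to urgent care, but Study Design and the Phase 2 procedures also name primary care and neurology practices.
- *That Aim 2 promises a randomised PES comparison.* Its heading says within-group, and its hypothesis is change from baseline in the RELAX arm. The added reference to MUC makes it ambiguous, no more. The Analysis Plan ties PES to the MS-migraine population; Table 2 lists it without that condition.
- *That the plan intends to set Phase 1 users against Phase 2 controls.* No section proposes this. The point is only that none rules it out.

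**Conclusion.** The concern holds in a limited form. Aim 1's randomised N of 400 is contradicted by the phase descriptions; the only randomised phase with a stated size has 90. The Phase 1 text contradicts itself on whether there were arms, and the stated total fits neither sum of approved or phase numbers. With 90 randomised, the detectable MIDAS-change difference is about 6.0 points, against about 2.8 with 400. This assumes SD 7, 1:1 allocation and half followed through in each arm.

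For MS-migraine and PTH, the supportable statement is that no randomised number is documented, so a between-arm conclusion in those populations has no stated basis. For Aim 2, the defect is ambiguity about the comparison. Whether any Phase 1 subjects were randomised cannot be settled from the documents, and the sponsor should say.

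**What to change.** - Correct the randomised N in Aim 1 to the Phase 2 number (90), unless randomisation in Phase 1 is documented, in which case state how many and in which populations.
- Reconcile Aim 1, the recruitment closures, the sample-size section (490, 402, 432, 90 and the reference to arms) and the Phase 1 and Phase 2 descriptions. Name the phase, population and N behind each comparison.
- State that every RELAX-versus-MUC comparison uses only subjects concurrently randomised to the two arms, and that single-arm Phase 1 data are reported separately.
- Say in Aim 2 which analyses are within-group and which are between-arm.
- Label the PES/MS-migraine and PTH results descriptive and within-group. If a randomised number in either population can be shown, restrict the comparison to those subjects.

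The changes are to wording only and need no new data. The price is that the stated randomised N falls and, unless randomised numbers are shown, the MS and PTH objectives become descriptive.

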The designated study team members will be trained to use the scripted protocol and treatment manual. The first four sessions of each member will be audio-recorded to assess treatment fidelity. Afterwards, one out of every ten will be audio-recorded to assess treatment fidelity.

If the study subject is in the RELAXaHEAD (Intervention) Group: The study team member will explain the rationale for PMR and load the RELAXaHEAD app onto the patients' smartphones.

Rationale (quoted from Smitherman T. and Penzien D. Headache: Advances in Psychotherapy 2014):

"As we discussed earlier, physical changes in our bodies associated with stress and arousal can produce headaches. Oftentimes, people say they are relaxed but their body still has a lot of tension that they do not recognize. It is important for you to learn how to 1) prevent your body from becoming tense;

2) recognize when your body becomes tense; and 3) truly relax your body and get rid of that tension.

Relaxation will help you learn to control physical arousal and thus help prevent headaches. Research has shown that learning relaxation leads to fewer and less intense headaches for most migraineand tension- type headache patients so long as they regularly use and practice their skills. This relaxation training program is going to teach you a specific set of procedures—not just 'trying to relax' on your own. You will learn to tense and then release various muscle groups throughout your body, step-by- step. By tensing your muscles first you can notice how different it feels to be truly relaxed. Over time you will be able to relax very quickly in almost any situation. Becoming skilled at relaxation will give you increased control over stress-related biological changes that cause headaches, and relaxation often produces many other positive changes."

PMR: The RA or RV will explain the rationale for PMR and download the application onto the subject's smartphones. The subject will perform PMR in the ED and discuss the optimal time and place to practice PMR at home.

Subjects will also enter their headache log daily on the app. The APP will track the amount of time playing the PMR. Subjects will be asked to do the following:

Intervention:

Week 1: 5 min deep breathing at least 5/7 days of the week

Week 2: 5 min PMR session at least 5/7 days of the week

Week 3: 15 min pmr preferred at least 5/7 days of the week

Week 4: pmr at least 4 days a week (optional body scan)

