Week 5: pmr at least 3 days a week (optional body scan)

Weeks 6-8: use when it is most helpful (falling asleep, HA coming on, stress)

The study intervention will be 8 weeks in duration but the full study length will be 6 months. There will be a baseline assessment (T0), a f/u call or email at one week (T1), a 30 day phone call or email assessment (T2), a 60 day phone call/email (T3), and a 90 day phone call/email (T4) (to examine persistence of effect after a month). The last follow up will be at 6 months to examine persistence of effect 4 months after the intervention ends. As we learned previously, we are adding the option for email as some subjects prefer email.

The MUC session is where the subjects are explained that in migraine treatment, they may be given medications to take to stop a migraine and medications to prevent a migraine. The mainstay of migraine management is a headache diary where people can track their headache days, headache intensity, medications taken, and any other details they think might be pertinent to share with their medical provider. No written material is provided during this session.

MUC: To match the time spent with the designated study team member, subjects will be given a general education session consisting of basic migraine information, such as evidence-based ways to treat headaches: treat early, limit acute medications < 2–3 days/week, and call the primary care physician (PCP) if abortive medications are used more frequently. They will be shown a website: https://[name].wixsite.com/relaxahead (to be renamed). The study team member will load the app onto the subject's smartphone but the PMR component will be blocked on the version of the app that the MUC subject receives.

All subjects will be asked to track headache frequency, intensity, and acute medication use on app. All subjects will get the post enrollment card after they have been enrolled so that they have some instructions on what to do when they go home.

All subjects will receive written educational material about migraine.³⁰ All subjects will receive follow-up phone calls, texts, and/or SendSafe emails at 1 week of enrollment and 1, 2, 3, and 6 months after study enrollment. (The choice of calls, texts or emails came from prior subjects who participated in IRB approved study focus groups.) The study team has permission from MCIT to send the following text messages (and an emailing indicating such approval is part of the submission process):

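### Aim 1's example adherence rule (4 days/week for 12 weeks) does not fit the 8-week, 60-day Phase 2 regimen, so the 70% adherence figure would mix non-use with correct following of the taper

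*Combined protocol and SAP*

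**What the plan says.** Aim 1 (Purpose of the Study) concerns participants randomised to RELAX or monitored usual care. Its adherence hypothesis, introduced as being about the PMR, is that "at least 70% of participants will be adherers (e.g., use RELAXaHEAD at least 4 days/week for 12 weeks". Aim 1 then names as its outcomes the "number of days of diary entered, number of days of pmr, time spent/day on pmr" and refers to Table 2.

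Table 2 lists as feasibility measures the percentage of patients doing PMR on 4 or more days in 7 (with no number of weeks), days with at least 5 minutes of PMR from the app's log, minutes per day, and reasons for non-adherence. It also says that the pain outcome will be adjusted for PMR adherence.

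Methods & Procedures sets the Phase 2 schedule:

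- It opens with breathing rather than PMR: "Week 1: 5 min deep breathing at least 5/7 days of the week".
- PMR starts the week after, with a 5-day minimum that week 3 repeats: "Week 2: 5 min PMR session at least 5/7 days of the week".
- The minimum then falls by one day: "Week 4: pmr at least 4 days a week (optional body scan".
- It falls by one more day in the last week that has a minimum: "Week 5: pmr at least 3 days a week (optional body scan".
- The rest of the intervention is as needed, with no number of days: "Weeks 6-8: use when it is most helpful (falling asleep, HA coming on, stress".

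The diary runs alongside: "Subjects will also enter their headache log daily on the app".

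The same section gives the intervention a length of 8 weeks. It limits Phase 2 app use to an initial 60 days, with the third month watched to see whether use continues. It also states that Phase 2 lasts 3 months. Payment for Participation pays for diary entries for up to 60 days. In the single-arm Phase 1, participants were asked to use the app for at least 3 months.

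**The concern.** An adherence rule should separate people who followed the assigned regimen from people who did not. Here the rule asks for a constant 4 days a week over 12 weeks, while the regimen tapers from week 4, has no stated minimum from week 6, and ends at 8 weeks. Someone who follows the taper exactly and someone who never opens the PMR module could both be scored non-adherent.

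Two results depend on the definition. The first is the adherence rate set against the 70% hypothesis, which is a main feasibility statement of Aim 1. The second is the pain analysis in Table 2: if its adjustment uses this rule, the covariate would carry the same misclassification. The rule also leaves open whether PMR or any app use is counted. The two readings can score the same participant differently, and the choice should not be left until the data have been seen.

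**Working it through.** **The plan's own figure.** The sample size text says that 30 patients per arm give an exact 95% interval with a lower bound above 50% if adherence is 70%. With 21 of 30 adherent (70%), the Clopper-Pearson lower bound is the 0.025 quantile of Beta(21, 10), which is 50.6%. With 20 of 30 it is 47.2%. The statement reproduces. The mismatch examined here does not change that arithmetic; it changes what the rate measures.

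**The rule.** 4 days/week × 12 weeks = 48 days, within 12 × 7 = 84 days.

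**The regimen, week by week** (Methods & Procedures; diary days counted over the initial 60 days):

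| Week | Assigned PMR minimum (days) | PMR minimum reaches 4? | Diary days requested |
|---|---|---|---|
| 1 | 0 (5 days of deep breathing) | no | 7 |
| 2 | 5 | yes | 7 |
| 3 | 5 | yes | 7 |
| 4 | 4 | yes | 7 |
| 5 | 3 | no | 7 |
| 6–8 | none stated | no | 7 each week |
| 9 | none stated | no | 4 |
| 10–12 | none stated | no | 0 |
| Total | 17 | 3 of 12 weeks | 60 |

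**Reading 1: the rule counts PMR.** The introduction to the hypothesis and Table 2's wording both favour this reading.

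- Assigned minimum: 5 + 5 + 4 + 3 = 17 days against 48. Counting week 1 breathing as well, 17 + 5 = 22.
- The minimum reaches 4 days in 3 of 12 weeks (4 of 12 with week 1 breathing).
- Minimums through week 5, then PMR every day from day 36: 17 + 21 = 38 days by day 56, and 17 + 25 = 42 by day 60. Both are below 48.
- Reaching 48 PMR days inside the 60 days, starting after week 1, needs 48/(60 − 7) = 48/53 = 0.906 of days, or 6.3 days a week.
- Table 2's threshold of 4 days in 7 also exceeds the week 5 minimum of 3, so it does not remove the conflict.

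**Reading 2: the rule counts any app use, including the diary.**

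- Sixty requested diary days exceed 48, so the total can be met. Completing 80% of the 60 days, the level at which the daily payment doubles, is 0.80 × 60 = 48 days.
- Week by week, 60 days = 8 weeks + 4 days, so weeks 1 to 9 can reach 4 days. The remaining 84 − 60 = 24 days, which include all of weeks 10 to 12, lie beyond the 60-day period.

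**The case against.** The strongest reply is that 12 weeks is not foreign to Phase 2. Methods & Procedures gives that phase a 3-month duration, and the change in MIDAS is measured at 3 months. Sustained use over that period is a legitimate, stricter bar for a feasibility study. This stands. A reader might infer that the window was simply carried over from Phase 1; it does match Phase 1, but the documents do not show that this is its source.

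A reader might also infer that nothing at all is asked of participants after day 60. That is too flat. The instruction to track headaches on the app, the contact after 3 days without a diary entry, and the weekly texts about PMR time carry no end date. They sit beside an explicit limit of 60 days, so the documents are not fully consistent. None of them sets a PMR minimum for weeks 10 to 12.

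Third, the rule is only an example within a hypothesis, and 17 against 48 is a floor. Every weekly target is a minimum, as-needed use in weeks 6 to 8 could be frequent, and Subject/Representative Comprehension speaks of a daily exercise. This limits any claim about the rate that will be observed. It does not supply another rule: no other adherence definition has a duration.

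Fourth, Aim 1's count outcomes and Table 2's reasons for non-adherence would help to tell non-users from participants who followed the taper. That is a real, partial mitigation.

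Finally, the 75% compliance figure and the 50% refinement threshold in the sample size text might be read as rival benchmarks. The first is a past-tense planning assumption, and the second stands under a Phase 1 heading. They call for a clarifying sentence at most.

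**Conclusion.** The point holds and should be fixed, with medium confidence. Aim 1's example rule and the Phase 2 regimen do not fit together. On the PMR reading, exact completion of the assigned minimums gives 17 of 48 days and is scored non-adherent. On the any-use reading, the total can be reached through the diary, but a weekly rule extends past the 60-day period. The 70% comparison would therefore mix non-use with correct following of the taper.

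The documents do not support the stronger conclusions that the rule cannot be met, or that the observed rate will necessarily be low. The distribution of use in weeks 6 to 12 is not given, so the effect on the rate is unknown. Counts of diary days, PMR days and PMR minutes are unaffected. The pain analysis is affected only if it adopts this definition.

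The conclusion assumes that Aim 1's hypothesis applies to the randomised Phase 2 RELAX arm, and that weeks without a stated minimum are counted as zero in the floor case.

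**What to change.** For the Phase 2 RELAX arm, score PMR adherence from the app's back-end log against the assigned schedule within the 8-week, 60-day period. One workable definition is at least 5, 5, 4 and 3 days in weeks 2, 3, 4 and 5 respectively, counting days with at least 5 minutes of PMR. Week 1 is left out because the documents do not say that deep breathing is logged. A set number of PMR days within 60 days would also be reasonable; what matters is that one rule is fixed before the data are examined.

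Apply the 70% hypothesis to that measure, and use the same definition where the pain analysis adjusts for PMR adherence. Report PMR use in weeks 6 to 8 and in month 3 descriptively as persistence. Keep 4 days/week for 12 weeks as a supplementary sustained-use summary, stating that it counts PMR. Add one sentence saying whether the 75% and 50% figures have any role in Phase 2, and one saying whether diary tracking and reminders stop at day 60.

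The cost is the wording of one endpoint and one covariate. No new data are needed, because the app records PMR time and Table 2 already lists days with at least 5 minutes. The downsides are slightly less comparability with Phase 1, which the supplementary summary partly restores, and that the stricter 12-week bar becomes secondary. The 70% figure was also set beside a different rule, so the sponsor should confirm that it still expresses the intended standard.
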